11. OUTCOME DETERMINATIONS

11.1 **Primary Endpoints**

This study will use co-primary endpoints

• Change in serum creatinine from randomization to 72 hours

• Area under the Curve (AUC) for Patient Global Assessment by VAS over 72 hours

Rationale for Primary Endpoints:

Change in creatinine from randomization to 72 hours was chosen as the primary safety endpoint due to the observed association between diuretic dosage and worsening renal function and the known association of worsening renal function with other adverse outcomes.

For the assessment of short term efficacy, a variety of endpoints have been utilized in prior AHF studies. These include patient self assessments of symptoms, typically either dyspnea or global well being (termed patient global assessment (PGA)). These self assessments are usually performed using a visual analog scale (VAS) or Likert scale. The DOSE-AHF study will use the PGA by VAS over 72 hours as the primary endpoint for efficacy. The rationale for this choice is that although dyspnea is the primary symptom for most patients with AHF, other symptoms (fatigue, edema, etc) may also be important and should be captured in the primary efficacy endpoint. We have chosen a patient symptom assessment r ather than other measures of diuretic efficacy such as weight change or urine output, because while these measures capture the pharmacodynamic effects of diuretic therapy, they may not be tightly correlated with other clinical events (such as rehospitalization or death), and are therefore not ideal surrogates in the assessment of efficacy.

Patients will be asked to self assess both their general well being and their level of dyspnea using a visual analog scale (VAS) method. For PGA, patients will mark their global well being on a 10 cm vertical line, with the top labeled "best you have ever felt" and the bottom labeled "worst you have ever felt". For dyspnea, the labels will be "I am not breathless at all" and "I am as breathless I have ever been". The VAS is scored from 0 to 100 but the patient is unaware of the numerical value of their response. Patients will self assess both PGA and dyspnea at randomization, 6, 12, 24, 48, 72, and 96 hours. The area under the curve for PGA assessment over the first 72 hours will be the primary efficacy endpoint (AUC for PGA VAS).

11.2 Secondary Endpoints

- *Weight Loss:* Weight loss will be measured over the 96 hour study period (at 24, 48, 72, and 96 hours from randomization).
- **Proportion of Patients Free of Congestion at 72 hours:** Freedom from congestion will be defined as JVP < 8 cm, no orthopnea, trace peripheral edema or less
- Change in the bivariate relationship of creatinine at 72 hours vs. weight loss at 72 hours: For each of the four treatment groups, weight loss at 72 hours and change in creatinine at 72 hours will be plotted on a two dimensional coordinate grid along with estimates of the mean effect and a 95% confidence ellipse. This will allow visual and statistical assessment of the "trade off" between change in weight and change in renal function. Comparisons among the 6

possible pairwise treatment differences will be constructed to detect differences between treatment strategies.

- Differences in Dyspnea VAS AUC over 24, 48, and 72 hours
- Differences in PGA VAS AUC over 24 and 48 hours
- Change in Serum Creatinine from baseline to 24, 48, 96 hours, day 7/discharge, and 60 days
- Change in Cystatin C from baseline to 72 hours, Day 7/discharge, and 60 days
- Worsening or persistent heart failure: defined as need for rescue therapy (additional open label loop diuretic, addition of thiazide, IV vasoactive agent for heart failure treatment, ultrafiltration, mechanical circulatory or respiratory support) over 72 hours after randomization
- **Development of Cardio-renal syndrome:** defined as increase in serum creatinine > 0.3 mg/dl from randomization at any time point during 72 hours after randomization
- **Treatment Failures**, a composite comprised of ANY ONE of the following during the 72 hours after randomization:
 - o development of cardio-renal syndrome as defined above
 - worsening/persistent heart failure as defined above
 - clinical evidence of over-diuresis requiring intervention (such as administration of IV fluids)
 - o death
- Net fluid loss over study period: Assessed at 24, 48, and 72 hours
- Time from randomization to discharge during index hospitalization
- Total days hospitalized for heart failure or deceased during the 60 days after randomization
- Changes in circulating biomarkers at 72 hours, day 7 (or discharge) and 60 days
- Death or rehospitalization (to include unscheduled clinic visits or ED visits) at 60 days

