2.3 Secondary Objectives

Other secondary objectives of this protocol will be to examine the effect of the above treatments on:

- Change in weight at 96 hours
- Freedom from signs and symptoms of congestion at 72 hours
- Change in bivariate vector of creatinine and weight at 72 hours
- Differences in Dyspnea VAS AUC over 24, 48 and 72 hours
- Differences in PGA VAS AUC over 24 and 48 hours
- Change in serum creatinine at 24, 48, 96 hrs, day 7 (or discharge), and day 60
- Change in cystatin C at 72 hours, day 7 (or discharge) and day 60
- Persistent or worsening heart failure
- Development of cardio-renal syndrome
- Treatment failure
- Time from randomization to discharge during index hospitalization
- Total days hospitalized for heart failure or dead within 60 days of randomization

DOSE protocol version 18.1; February 4, 2008

• Changes in circulating biomarkers from baseline to 72 hours, day 7 (or discharge), and day 60

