6. STUDY POPULATION AND ELIGIBILITY CRITERIA

6.1 Inclusion Criteria

- Male or female patient \geq 18 years old
- Prior clinical diagnosis of heart failure with daily home use of oral loop diuretic for at least one month
- Daily oral dose of furosemide \geq 80 mg and \leq 240 mg (or equivalent)
- Must be identified within 24 hours of hospital admission
- A diagnosis of heart failure as defined by the presence of at least 1 symptom (dyspnea, orthopnea, or edema) AND 1 sign (rales on auscultation, peripheral edema, ascites, pulmonary vascular congestion on chest radiography)
- Anticipated need for IV loop diuretics for at least 48 hours
- Willingness to provide informed consent

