6.2 Exclusion Criteria

- BNP < 250 ng/ml or NT-proBNP <1000 mg/ml
- Received IV vasoactive treatment or ultra-filtration therapy for heart failure since initial presentation
- Anticipated need for IV vasoactive treatment or ultra-filtration for heart failure during this hospitalization
- Substantial diuretic response to pre-randomization diuretic dosing such that higher doses of diuretics would be contra-indicated (based on investigator judgment)
- Systolic BP <90 mmHg
- Serum creatinine >3.0 mg/dl at baseline or renal replacement therapy
- Hemodynamically significant arrhythmias
- Acute coronary syndrome within 4 weeks
- Active myocarditis
- Hypertrophic obstructive cardiomyopathy
- Severe stenotic valvular disease
- Restrictive or constrictive cardiomyopathy
- Complex congenital heart disease
- Constrictive pericarditis

- Non-cardiac pulmonary edema;
- Clinical evidence of digoxin toxicity;
- Need for mechanical hemodynamic support
- Sepsis
- Terminal illness (other than HF) with expected survival of less than 1 year
- Previous adverse reaction to the study drugs
- Use of IV iodinated radiocontrast material in last 72 hours or planned during hospitalization
- Enrollment or planned enrollment in another randomized clinical trial during this hospitalization
- Inability to comply with planned study procedures

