9.2 Baseline Assessments

At the time of randomization, all study subjects will undergo

- Directed history and physical examination, focused on signs and symptoms of congestion
- Vital signs (including O₂ saturation and weight)
- Concomitant cardiovascular medications
- Creatinine, BUN, and electrolytes (local laboratory)
- Patient Global Well being assessment (PGA) by VAS (see Appendix C)
- Dyspnea assessment by VAS (see Appendix C)
- Blood sample for biomarkers core laboratory

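### Entry criteria and the 72-hour freedom-from-congestion definition use different items, so a patient can enter already meeting this secondary endpoint; the analysis should account for baseline status

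*Protocol*

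**What the plan says.** - **Endpoint (Protocol 11.2).** The endpoint is titled "Proportion of Patients Free of Congestion at 72 hours" and defined by three items: "Freedom from congestion will be defined as JVP < 8 cm, no orthopnea, trace peripheral edema or less". It is read at 72 hours. Nothing limits it to patients who were congested at entry, and no adjustment for baseline status is mentioned.
- **Objective (Protocol 2.3).** "Freedom from signs and symptoms of congestion at 72 hours".
- **Entry (Protocol 6.1).** The diagnosis requires "presence of at least 1 symptom (dyspnea, orthopnea, or edema) AND 1 sign", and the qualifying signs are "1 sign (rales on auscultation, peripheral edema, ascites, pulmonary vascular congestion on chest radiography".
- **Other entry filters.** Section 6.1 also requires at least a month of home loop diuretic, a daily furosemide dose of 80 to 240 mg or equivalent, and an expected need for IV loop diuretic of at least 48 hours. Section 6.2 excludes "BNP < 250 ng/ml or NT-proBNP <1000 mg/ml" and patients who responded substantially to diuretic before randomization.
- **Baseline examination (Protocol 9.2).** At randomization every patient has a "Directed history and physical examination, focused on signs and symptoms of congestion".
- **Analysis (Protocol 14.4).** No method is named for this endpoint. A general sentence puts the emphasis on comparing the randomized groups.

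**The concern.** The two lists overlap only in part. Orthopnea and edema are on both. JVP is in the endpoint but not among the entry signs. Dyspnea, rales, ascites and radiographic congestion can qualify a patient for entry but play no part in the endpoint. A patient can therefore be recruited on items that the endpoint ignores, while having none of the items that it measures.

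Such a patient has no congestion, as the endpoint defines it, left to relieve. If these patients mostly stay free whatever they are given, they add the same number of successes to each arm and pull the observed difference towards zero. Both factors are affected, because the endpoint serves the dose comparison and the route comparison alike. What is at stake is sensitivity on one secondary endpoint: a real difference in clearing congestion would look smaller and be easier to miss.

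**Working it through.** **1. Can a patient be eligible and already free of congestion?**

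| Item | Counts for entry (6.1) | In the endpoint (11.2) |
|---|---|---|
| Dyspnea | yes, symptom | no |
| Orthopnea | yes, symptom | yes |
| Edema | yes, symptom and sign | yes (more than trace) |
| Rales | yes, sign | no |
| Ascites | yes, sign | no |
| Pulmonary vascular congestion | yes, sign | no |
| JVP | no | yes (8 cm or more) |

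Treat each of the seven items as present or absent, with edema meaning more than trace: 2^7 = 128 patterns.
- Eligible with edema: 2^6 = 64.
- Eligible without edema: 3 (dyspnea, orthopnea or both) × 7 (at least one of three signs) × 2 (JVP) = 42.
- Total eligible: 64 + 42 = 106.
- Eligible and already free: dyspnea present; orthopnea, edema and raised JVP absent; at least one of rales, ascites and pulmonary vascular congestion. That is 2^3 − 1 = 7 patterns.

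So the overlap is real. The count is of patterns, not patients, and says nothing about how often they occur.

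**2. The plan's own figures.** The protocol states no rate, effect size or power for this endpoint, so there is none to reproduce. Its creatinine calculation does reproduce: 150 per level, difference 0.20 mg/dL, SD 0.5, two-sided 2.5% gives 88.9% against the stated 88%. I use the same 150 per level (300 patients, 2×2 factorial) and the default 5% level of section 14.1, taken as two-sided.

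**3. Dilution.** Let f be the fraction free at baseline, r their probability of still being free at 72 hours (the same in both arms), and p1 and p2 the 72-hour rates among patients congested at entry. The crude rates are f·r + (1 − f)·p1 and f·r + (1 − f)·p2. Their difference is (1 − f)(p2 − p1), whatever r is.

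**4. Power.** With n = 150, crude rates P1 and P2, d = P2 − P1 and m = (P1 + P2)/2:

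power = Φ{ [d − 1.96·√(2m(1 − m)/n)] / √([P1(1 − P1) + P2(1 − P2)]/n) }.

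Example at f = 10%, r = 1, assumed 15% v 30%: P1 = 0.10 + 0.90 × 0.15 = 0.235; P2 = 0.10 + 0.90 × 0.30 = 0.370; d = 0.135; m = 0.3025. The two square roots are 0.0530 and 0.0525. Power = Φ[(0.135 − 0.1040)/0.0525] = Φ(0.59) = 72%.

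The congested-only columns use 150(1 − f) per level at the undiluted rates. Both rate pairs are assumptions.

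| f | Crude, 15% v 30% | Congested only | Crude, 20% v 35% | Congested only |
|---|---|---|---|---|
| 0 | 88% | 88% | 83% | 83% |
| 2% | 85% | 87% | 81% | 83% |
| 5% | 80% | 86% | 76% | 81% |
| 10% | 72% | 84% | 69% | 79% |
| 20% | 57% | 80% | 56% | 74% |

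**5. Stratifying instead of restricting.** I simulated 100,000 trials per setting (150 per level, 15% v 30% among the congested, f = 10%), using the Mantel-Haenszel chi-square without continuity correction.

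| Baseline-free patients still free at 72 h | Crude | Congested only | All patients, stratified |
|---|---|---|---|
| 100% v 100% | 73% | 85% | 85% |
| 90% v 90% | 74% | 85% | 83% |
| 80% v 95% | 82% | 85% | 89% |

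Stratifying recovers most or all of the loss while keeping every randomized patient. It does better than restriction when staying free differs between arms.

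**The case against.** **The objective is a state, not a change.** A reader might infer that the endpoint contradicts its objective because it mixes relief with absence at entry. Section 2.3 does not support that: it asks for freedom at 72 hours, which a 72-hour proportion measures. Relief of symptoms belongs to the co-primary global well-being hypotheses in 2.1 and 2.2. This objection stands, and the point is one of efficiency rather than contradiction.

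**The fraction is probably small.** All three endpoint items must be absent together in a patient admitted despite substantial home diuretic, with a natriuretic peptide above the threshold and an expected 48 hours of IV treatment. This stands. A reader might take the 57% at f = 20% as the trial's likely power; nothing in the protocol supports one patient in five. At f = 2% the crude analysis loses about 3 points under 15% v 30%.

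**Baseline-free patients can still respond.** A reader might infer that they cannot show any effect of dose or route. They can become congested by 72 hours, perhaps at different rates by arm. With 80% v 95% staying free, the crude difference is 0.15f + 0.15(1 − f) = 15 points at every f, with no shrinkage. The (1 − f) factor therefore needs similar retention across arms. This stands, and it is why restricting the denominator should not be the main analysis.

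**Persisting dyspnea or rales.** Dyspnea has its own VAS endpoint, and heart failure needing rescue therapy is captured separately in 11.2. The choice of items is not challenged here.

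**It belongs in the SAP.** The SAP is not at hand and may already adjust for baseline status. But 11.2 itself fixes the definition and refers to no baseline, whereas the creatinine and cystatin C endpoints beside it are stated as changes from baseline. The clarification is worth making there.

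**Conclusion.** The point holds in limited form. On the protocol's wording, patients can be enrolled who already meet the freedom-from-congestion definition, and no other criterion rules them out. If they stay free at similar rates in all arms, the crude risk difference for each factor is multiplied by (1 − f). Under an assumed 15% v 30% among patients congested at entry, crude power goes from 88% to about 85%, 80% or 72% at f = 2%, 5% or 10%. Neither f nor the rates are in the protocol, and f is probably towards the low end.

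A reader might infer that the comparison is biased or that the trial's main conclusions are at risk. Neither follows. Baseline status precedes randomization, so any imbalance is due to chance, and the effect is dilution. The co-primary endpoints, the sample size and the type I error are untouched. This is a low-cost improvement to one secondary endpoint.

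**What to change.** In section 11.2, add that the same three items (JVP, orthopnea, peripheral edema) will be scored from the examination at randomization. State that the 72-hour proportion will be analysed in all randomized patients, stratified by or adjusted for whether the definition was met at baseline. Report the comparison restricted to patients congested at baseline as a supporting analysis, together with the number already free at baseline in each arm.

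The eligibility criteria and the endpoint definition stay as they are. The cost is a sentence or two in 11.2 and a check that the baseline case report form records the three items in the same form as at 72 hours; the congestion examination itself is already scheduled in 9.2. If few patients prove to be free at baseline, the adjusted and crude results will nearly coincide and little is lost.

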5. BASIC STUDY DESIGN

This study will be a randomized, controlled, multi-center clinical trial of patients with signs and symptoms consistent with AHF within 24 hours of hospital admission. A total of 300 patients will be enrolled in the trial.

Patients will be randomized to one of 4 treatment regimens (75 patients / treatment regime) defined by a 2x2 factorial treatment design:

1) "High intensification" strategy for IV furosemide (defined as 2.5 x stable PO home dose) vs. "low intensification" dose IV furosemide (defined as 1 x stable PO home dose). This treatment will be double-blinded.

2) Continuous furosemide IV infusion vs. IV furosemide given as IV bolus Q12 hours. This treatment will be double-blinded.

The study treatment regimen will be administered from randomization through 48 hours, at which point the investigator may modify the IV loop diuretic strategy based on clinical assessment of the patient and their response to therapy. Permitted modifications will be:

- 1. Continue current strategy without change
- 2. Increase dose by 50% (while remaining blinded to both dose and route of administration assignment)
- 3. Switch to oral furosemide (dose at the investigator's discretion) in preparation for discharge.

Blinding of initial treatment assignment will be maintained regardless of which of the options are selected.

After 72 hours, all diuretic treatment will be open label at the treating physician's discretion.

The primary assessment for both efficacy and safety will occur at 72 hours after randomization.

The primary endpoint for efficacy will be patient reported global well being by visual analog scale (VAS) quantified as the area under the curve (AUC) over 72 hours.

The primary safety endpoint will be change in serum creatinine from baseline to 72 hours.

Anticipated need for at least 48 hours of IV diuretic therapy will be an inclusion criterion for the study. However, if patients are deemed to have achieved adequate diuresis before 48 hours, they may be switched to oral dosing of diuretics (open label) at the investigators discretion. If patients are discharged prior to 72 hour assessment, the last VAS

DOSE protocol version 18.1; February 4, 2008

assessment and last serum creatinine will be carried forward to 72 hours for the purposes of assessing the primary endpoints.

If patients die prior to 72 hour assessment, the last serum creatinine will be carried forward and the last VAS will be imputed as 0.

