9.1 Randomization

After providing informed consent and signing the ICF, all study subjects will be randomized using procedures determined by the DCC to one of 4 treatment groups, based on the 2 x 2 factorial design defined above. Randomization will be 1:1:1:1. Blocking will be used to ensure relatively equal distribution of patients to each arm. Randomization will be stratified by clinical site.

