14. STATISTICAL CONSIDERATIONS

14.1 Overview

Means, standard deviations, medians, 25th and 75th percentiles will be presented for continuous variables; the number and frequency of patients in each category will be presented for nominal variables. Statistical tests with a p value < 0.05 will be considered statistically significant, unless otherwise stated. Analyses will be performed using SAS software (SAS Institute, Inc, Cary, NC).

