14.3.1 Change in Creatinine at 72 hours

The standard deviation observed for the change in creatinine from baseline to discharge in the ESCAPE trial (unpublished data) was 0.47 mg/dL. Similarly, in the control arm of the UNLOAD study (unpublished data), the standard deviation of the change in creatinine from baseline to discharge was 0.5 mg/dL. With 300 patients, we will have approximately 88% power to detect a difference in mean creatinine of 0.20 mg/dL for each main comparison, assuming a standard deviation of 0.5 mg/dL. Assuming a smaller standard deviation of 0.4 mg/dL, we would have approximately 98% power to detect a difference of 0.2 mg/dL. The effect of various standard deviations on the power to detect given mean differences in peak creatinine (mg/dL) at the 2.5% significance level is given in Figure 5.

Figure 5. Power with 150 patients per group to detect various mean differences in creatinine (mg/dL) assuming normal distribution with various standard deviations at the two-sided 2.5% significance level

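### The bivariate creatinine-weight endpoint is given only six 75 v 75 cell-pair comparisons; the dose and route contrasts (150 v 150) that match the objectives are not named

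*Protocol*

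**What the plan says.** Protocol section 5 sets the design: "Patients will be randomized to one of 4 treatment regimens (75 patients / treatment regime) defined by a 2x2 factorial treatment design". Section 9.1 gives equal allocation ("Randomization will be 1:1:1:1"), so each factor compares 150 patients with 150. The power figure in section 14.3.1 uses that size: "Power with 150 patients per group to detect various mean differences in creatinine".

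Sections 2.1 and 2.2 pose two questions, dose and route. Section 2.3 carries those same treatments into the secondary objectives, including the bivariate endpoint. Section 14.3 assumes no interaction.

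For the bivariate endpoint, section 11.2 works by cell: "For each of the four treatment groups, weight loss at 72 hours and change in creatinine at 72 hours will be plotted", with mean estimates and 95% ellipses. It promises a statistical as well as a visual assessment, and the only comparisons it names are these: "Comparisons among the 6" "possible pairwise treatment differences will be constructed to detect differences between treatment strategies".

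Section 11.2 states no significance level or adjustment for the six. Section 14.1 supplies a default: "Statistical tests with a p value < 0.05 will be considered statistically significant, unless otherwise stated". The one Bonferroni step, in section 14.3, is for the two co-primary endpoints.

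**The concern.** Four cells give 4 × 3 / 2 = 6 pairs. Two change dose at a fixed route, two change route at a fixed dose, and two change both. Each of the first four answers a factor question with half of the patients available for it. The last two isolate neither factor. In scenario 1 of the protocol's Table 1, low dose by bolus and high dose by infusion have the same mean creatinine (0.3), so that pair shows no difference although both factors act.

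This endpoint is meant to show the trade-off between weight change and renal function. If the six pairs are its only tests, a dose or route effect on the trade-off is judged less efficiently than the design allows. The reader must also combine several partly overlapping tests into an answer that one contrast per factor would give directly.

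**Working it through.** **1. The protocol's own figure.** Inputs from section 14.3.1: difference 0.20 mg/dL, SD 0.5, 150 per group, two-sided 0.025. Power ≈ Φ(δ / (SD·√(2/n)) − z).
- 0.20 / (0.5·√(2/150)) = 3.464; 3.464 − 2.241 = 1.223; power 88.9%. The stated 88% is reproduced.

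**2. Creatinine alone, same effect.**
- 150 v 150 at 0.05: 3.464 − 1.960 = 1.504; power 93.4%.
- 75 v 75 at 0.05: 0.20 / (0.5·√(2/75)) = 2.449; 2.449 − 1.960 = 0.489; power 68.8%.
- 75 v 75 at 0.05/6: 2.449 − 2.638 = −0.189; power 42.5%.

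**3. Bivariate test.** The protocol names no test, so Hotelling T² is assumed. It gives no weight effect, weight SD or correlation, so these are assumed and varied. With standardised shifts d_c (creatinine) and d_w (weight) and correlation ρ:

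D² = (d_c² − 2ρ·d_c·d_w + d_w²) / (1 − ρ²), and noncentrality = (n/2)·D², referred to a noncentral F with 2 numerator df.

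Base case: d_c = 0.20/0.5 = 0.4, d_w = 0, ρ = 0, so D² = 0.16. Noncentrality is 6 for n = 75 and 12 for n = 150. If weight also shifts 0.4 SD, D² = 0.32.

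| Scenario | 75 v 75, α 0.05 | 75 v 75, α 0.05/6 | 150 v 150, α 0.05 | 150 v 150, α 0.025 |
|---|---|---|---|---|
| Creatinine only, ρ = 0 | 57% | 31% | 88% | 81% |
| Both shift 0.4 SD, ρ = 0 | 88% | 68–69% | >99% | 99% |
| Range: d_w 0 to 0.4, ρ −0.3 to 0.3 | 58–97% | 32–88% | 88 to >99% | 81 to >99% |

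The range row pools the covariance over all four cells (296 df). The 57% and 31% use only the two cells compared (148 df); with pooling they are 58% and 32%.

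**4. Same decision on both sides.** The two same-route dose pairs share no patients. In the base case:
- Power that at least one is significant at 0.05: 1 − (1 − 0.575)² = 82%.
- Error of that rule when dose has no effect: 1 − 0.95² = 9.75%.
- The single 150 v 150 contrast has 88% power at 5% error.

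**5. Chance of any false positive when no cells differ** (200,000 simulated trials, four cells of 75):
- Six pairs at 0.05: 20.8%.
- Six pairs at 0.05/6: 4.2%.
- Two factor contrasts at 0.05 each: 9.6%.
- Two factor contrasts at 0.025 each: 4.9%.

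**The case against.** Four points on the other side carry weight.

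- **Adjustment.** A reader might infer that the protocol prescribes unadjusted testing of the six pairs. It does not: section 11.2 is silent, and the section 14.1 default applies only where nothing else is stated. Multiplicity for a secondary endpoint is commonly left to the SAP, so the 21% is conditional on that default. Adjustment does not rescue the pairs, however, because it lowers per-pair power to 31% in the base case.
- **Factor analyses elsewhere.** A reader might infer that dose and route contrasts are ruled out. Nothing excludes them. Section 14.4 speaks of comparing the groups formed by randomization, which fits cells or factors. Section 14.2 models creatinine change at 72 hours by the two main effects, and section 14.4 plans linear models for weight. Each component can therefore be examined by factor; what lacks a named factor-level test is the joint outcome.
- **Size of the power loss.** Setting 57% beside 21% would suggest that both describe one decision rule. They do not: the first is for a single pair, the second for all six. In the base case, at least one of the four pairs that differ in dose is significant in 89% of simulated trials, about the same as the contrast. That rule's error under the null lies above the 9.75% of the two pairs it contains and below the 21% of the six it belongs to. The 57% also lies at the low end of the assumed range.
- **Purpose.** Section 11.2 speaks of treatment strategies, and the executive summary lists four regimens. Comparing cells is reasonable as a description of where each regimen falls, and it becomes more useful if the factors interact. The protocol, however, assumes that they do not.

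**Conclusion.** The point holds as a matter of efficiency and fit to the objectives. Section 11.2 names six 75 v 75 comparisons as the only inference for the bivariate endpoint and omits the two contrasts that the factorial design supports. On a like-for-like rule in the base case, the pairs give 82% power at about 10% error, where one contrast gives 88% at 5%. Over the assumed range of weight effects and correlations, a single pair is always weaker than the contrast, but the gap narrows as the joint shift grows. These figures rest on Hotelling T², 75 patients per cell with no missing data, additivity, and assumed values for everything concerning weight.

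The documents do not support the stronger conclusion that the plan commits to a 21% false-positive rate, or that a real dose effect would probably be missed. No primary conclusion depends on this endpoint, which is one of many secondary ones. The priority is low.

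**What to change.** In section 11.2, name high v low intensification and infusion v bolus, each 150 v 150, as the tests of the bivariate endpoint, using Hotelling T² or a linear model with both outcomes. State the level. At 0.05 each, the two contrasts still give about a 10% chance of some false positive; at 0.025 each it is about 5%, with 81% power in the base case. Keep the four cell means, the 95% ellipses and the six pairwise differences as description, without significance claims.

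The cost is analysis wording only: no added patients, data or procedures. The downside is that individual regimens can no longer be declared different on this endpoint, and that the contrasts rely on the additivity already assumed in section 14.3. The retained cell display would help a reader to see whether that assumption looks doubtful.
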